8.1.2 Laboratory test abnormalities

8.1.2.1 Definitions and reporting

Laboratory abnormalities that constitute an Adverse event in their own right (are considered clinically significant, induce clinical signs or symptoms, require concomitant therapy or require changes in study treatment), should be recorded on the Adverse Events CRF. Whenever possible, a diagnosis, rather than a symptom should be provided (e.g., anemia instead of low hemoglobin). Laboratory abnormalities that meet the criteria for Adverse Events should be followed until they have returned to normal or an adequate explanation of the abnormality is found. When an abnormal laboratory or test result corresponds to a sign/symptom of an already reported adverse event, it is not necessary to separately record the lab/test result as an additional event.

Laboratory abnormalities, that do not meet the definition of an adverse event, should not be reported as adverse events. A Grade 3 or 4 event (severe) as per CTCAE does not automatically indicate a SAE unless it meets the definition of serious as defined below and/or as per investigator's discretion. A dose hold or medication for the lab abnormality may be required by the protocol in which case the lab abnormality would still, by definition, be an adverse event and must be reported as such.

8.1.3 Adverse events of special interest

Adverse events of special interest (AESI) are defined as events (serious or non-serious) which are ones of scientific and medical concern specific to the sponsor's product or program, for which ongoing monitoring and rapid communication by the investigator to the sponsor may be

appropriate. Such events may require further investigation in order to characterize and understand them.

Adverse events of special interest are defined on the basis of an ongoing review of the safety data. AESIs are discussed in detail in the Investigator's Brochure.

AESIs for this trial include hepatic toxicity, hypertension, thyroid-related disorders and cardiac disorders.

8.2 Serious adverse events

8.2.1 Definitions

Serious adverse event (SAE) is defined as one of the following:

- Is fatal or life-threatening
- Results in persistent or significant disability/incapacity
- Constitutes a congenital anomaly/birth defect
- Is medically significant, i.e., defined as an event that jeopardizes the patient or may require medical or surgical intervention to prevent one of the outcomes listed above
- Requires inpatient hospitalization or prolongation of existing hospitalization,
- Note that hospitalizations for the following reasons should not be reported as serious adverse events:
 - Routine treatment or monitoring of the studied indication, not associated with any deterioration in condition
 - Elective or pre-planned treatment for a pre-existing condition that is unrelated to the indication under study and has not worsened since signing the informed consent
 - Social reasons and respite care in the absence of any deterioration in the patient's general condition
- Note that treatment on an emergency outpatient basis that does not result in hospital admission and involves an event not fulfilling any of the definitions of a SAE given above is not a serious adverse event
- Progression of malignancy (including fatal outcomes), if documented by use of appropriate method (i.e. as per RECIST criteria), should not be reported as a serious adverse event.

8.2.2 Reporting

To ensure patient safety, every SAE, regardless of suspected causality, occurring after the patient has provided informed consent and until at least 30 days after the patient has stopped study treatment must be reported to Novartis within 24 hours of learning of its occurrence.

Any additional information for the SAE including complications, progression of the initial SAE, and recurrent episodes must be reported as follow-up to the original episode within 24 hours of the investigator receiving the follow-up information. An SAE occurring at a different time interval or otherwise considered completely unrelated to a previously reported one should be reported separately as a new event.

Any SAEs experienced after the 30 day safety evaluation follow-up period should only be reported to Novartis if the investigator suspects a causal relationship to the study treatment.

Information about all SAEs is collected and recorded on the Serious Adverse Event Report Form; all applicable sections of the form must be completed in order to provide a clinically thorough report. The investigator must assess and record the relationship of each SAE to each specific study treatment (if there is more than one study treatment), complete the SAE Report Form in English, and submit the completed form within 24 hours to Novartis. Detailed instructions regarding the SAE submission process and requirements for signatures are to be found in the investigator folder provided to each site.

Follow-up information is submitted in the same way as the original SAE Report. Each re-occurrence, complication, or progression of the original event should be reported as a follow-up to that event regardless of when it occurs. The follow-up information should describe whether the event has resolved or continues, if and how it was treated, whether the blind was broken or not, and whether the patient continued or withdrew from study participation.

If the SAE is not previously documented in the Investigator's Brochure or Package Insert (new occurrence) and is thought to be related to the Novartis study treatment, an oncology Novartis Chief Medical Office and Patient Safety (CMO&PS) department associate may urgently require further information from the investigator for Health Authority reporting. Novartis may need to issue an Investigator Notification (IN), to inform all investigators involved in any study with the same drug that this SAE has been reported. Suspected Unexpected Serious Adverse Reactions (SUSARs) will be collected and reported to the competent authorities and relevant ethics committees in accordance with Directive 2001/20/EC or as per national regulatory requirements in participating countries.

8.3 Emergency unblinding of treatment assignment

Not applicable.

8.4 Pregnancies

To ensure patient safety, each pregnancy occurring while the patient is on study treatment must be reported to Novartis within 24 hours of learning of its occurrence. The pregnancy should be followed up to determine outcome, including spontaneous or voluntary termination, details of the birth, and the presence or absence of any birth defects, congenital abnormalities, or maternal and/or newborn complications.

Pregnancy should be recorded on a Clinical Trial Pregnancy Form and reported by the investigator to the oncology Novartis Chief Medical Office and Patient Safety (CMO&PS). Pregnancy follow-up should be recorded on the same form and should include an assessment of the possible relationship of pazopanib to any pregnancy outcome. Any SAE experienced during pregnancy must be reported on the SAE Report Form.

Pregnancy outcomes should be collected for the female partners of any males who took study treatment in this study. Consent to report information regarding these pregnancy outcomes should be obtained from the mother.

The collection of this information could last up until to birth and potentially up to 12 months following the birth of the child in some cases.

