21. Other severe acute or chronic medical or psychiatric condition or laboratory abnormality that may increase the risk associated with study participation or study drug administration, or may interfere with the interpretation of study results, and in the judgment of the investigator would make the subject inappropriate for entry into the study.
22. Pregnant or nursing (lactating) women
23. Women of child-bearing potential, defined as all women physiologically capable of becoming pregnant, are excluded **unless** they are using highly effective methods of contraception during dosing and for 2 weeks after stopping medication. Highly effective contraception methods include:
- Total abstinence (when this is in line with the preferred and usual lifestyle of the subject. Periodic abstinence (e.g., calendar, ovulation, symptothermal, post-ovulation methods) and withdrawal are not acceptable methods of contraception
 - Female sterilization (have had surgical bilateral oophorectomy with or without hysterectomy), total hysterectomy, or tubal ligation at least six weeks before taking study treatment. In case of oophorectomy alone, only when the reproductive status of the woman has been confirmed by follow up hormone level assessment
 - Male sterilization (at least 6 months prior to screening). The vasectomized male partner should be the sole partner for that subject
 - Use of oral, injected or implanted hormonal methods of contraception or placement of an intrauterine device (IUD) or intrauterine system (IUS), or other forms of hormonal contraception that have comparable efficacy (failure rate <1%), for example hormone vaginal ring or transdermal hormone contraception.

In case of use of oral contraception women should have been stable on the same pill for a minimum of 3 months before taking study treatment.

Women are considered post-menopausal and not of child bearing potential if they have had 12 months of natural (spontaneous) amenorrhea with an appropriate clinical profile (i.e., age appropriate, history of vasomotor symptoms) or have had surgical bilateral oophorectomy (with or without hysterectomy), total hysterectomy, or tubal ligation at least six weeks ago. In the case of oophorectomy alone, only when the reproductive status of the woman has been confirmed by follow up hormone level assessment is she considered not of child bearing potential.

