24. Sexually active males unless they use a condom during intercourse while taking the drug during treatment and for 2 weeks after stopping treatment and should not father a child in this period. A condom is required to be used also by vasectomized men as well as during intercourse with a male partner in order to prevent delivery of the drug via semen.
25. Patients with known immediate or delayed hypersensitivity reaction or idiosyncrasy to drugs chemically related to pazopanib.

6 Treatment

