7.2.2.5.8 Pregnancy testing

Serum pregnancy tests are required at screening and end of treatment for women of child-bearing potential.

Monthly urine pregnancy testing is required during treatment for women of child-bearing potential. Urine pregnancy tests for use during on-site visits will be supplied by the central lab and will be performed locally during site visits on Day 1 of Cycles 2 through 6. After Cycle 6, women of child-bearing potential will be required to perform monthly at-home urine pregnancy tests. At-home pregnancy test kits will be supplied by the investigator. Patients who administer the urine pregnancy test at home will complete a simple diary with the dates and outcome of the urine pregnancy test while on study treatment. Patients should be instructed to bring the diary with them to every visit.

Please refer to the [Section 5.3](#) for the definition of women of child-bearing potential.

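### For female patients, the pregnancy reporting rule in Protocol 8.4 stops at the end of treatment, two weeks before the contraception period in 5.3 ends

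*Protocol*

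**What the plan says.** Protocol 8.4 sets the reporting duty: "each pregnancy occurring while the patient is on study treatment must be reported to Novartis within 24 hours of learning of its occurrence". The same section asks for follow-up to outcome on the Clinical Trial Pregnancy Form. Since Amendment 2, that collection may continue for up to 12 months after the birth. No extension beyond treatment is stated for a female patient. For male patients 8.4 adds "Pregnancy outcomes should be collected for the female partners of any males who took study treatment in this study", with no time limit.

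Protocol 5.3 sets the contraception period. Criterion 23 excludes women of child-bearing potential unless "they are using highly effective methods of contraception during dosing and for 2 weeks after stopping medication". Criterion 24 requires condom use by sexually active men during treatment and "for 2 weeks after stopping treatment and should not father a child in this period".

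Protocol 7.2.2.5.8 sets the testing: "Serum pregnancy tests are required at screening and end of treatment for women of child-bearing potential", and "Monthly urine pregnancy testing is required during treatment for women of child-bearing potential". No test is scheduled after end of treatment.

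Protocol 7.1.5.1 requires safety evaluation of every patient for 30 days after the last dose. Protocol 8.2.2 requires SAEs to be reported until at least 30 days after treatment stops, and later ones only where the investigator suspects that study treatment caused them.

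**The concern.** By asking for contraception after the last dose, the protocol treats those two weeks as a period in which a pregnancy matters. The rule that would bring such a pregnancy to the sponsor's attention ends earlier, with treatment. A site that follows 8.4 to the letter has no duty to report, within 24 hours or at all under that section, a conception nine or ten days after a woman's last tablet. It would not have to complete the pregnancy form, follow the pregnancy to outcome or follow the infant.

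What is at stake is the completeness of exposure-in-pregnancy data. Miscarriages, terminations and normal births after a conception in this window could go unrecorded as pregnancy outcomes. No efficacy estimate, analysis set or sample-size figure depends on this.

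**Working it through.** The plan gives no figure to reproduce. The check sets the post-treatment windows side by side, counting days after the last dose.

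| Rule | Source | Days covered after last dose |
|---|---|---|
| Contraception, women | Protocol 5.3, criterion 23 | 2 × 7 = 14 |
| Safety evaluation | Protocol 7.1.5.1 | 30 |
| SAE reporting regardless of causality | Protocol 8.2.2 | at least 30 |
| 24-hour pregnancy report, female patients | Protocol 8.4 | 0 |
| Scheduled pregnancy tests | Protocol 7.2.2.5.8 | none after the end-of-treatment test |

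1. Gap between the contraception period and the pregnancy rule: 14 − 0 = 14 days for each woman of child-bearing potential.
2. Existing safety contact: the 30-day period spans the whole gap and runs 30 − 14 = 16 days past it. A contact at which the question could be asked is therefore already in the schedule.
3. Testing: a test cannot detect a conception that happens after it. If the end-of-treatment test falls d days after the last dose (d no more than 14), then 14 − d days of the window follow the last scheduled test. Appendix 2, section 4.2, puts that visit within 7 days of the last treatment, which would leave at least 14 − 7 = 7 days. That appendix is a general guideline, so the 7 days are illustrative. The 14-day gap in step 1 does not depend on them.
4. Active enquiry: Section 7.1.5.1 lists the forms to be updated in safety follow-up. They cover adverse events, surgical and medical procedures, concomitant medications and subsequent antineoplastic therapy. None is for pregnancy.
5. Other routes by which such a pregnancy could surface:
   - Safety follow-up (7.1.5.1): reaches all patients, but only if the woman mentions the pregnancy.
   - Efficacy follow-up (4.1.4 and 7.1.5.2): pregnancy is a listed reason for ending this phase and is recorded on the disposition page. The phase applies only to patients who stop without progression before one year from LPFV, and it yields a reason for leaving, not an outcome.
   - SAE reporting (8.2.1 and 8.2.2): a birth defect is an SAE, but a birth would come long after day 30, when reporting depends on suspected causality. An uncomplicated pregnancy is not an SAE.

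None of these routes starts the 24-hour clock in 8.4, the pregnancy form or infant follow-up.

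**The case against.** The strongest reply is that this is a one-clause mismatch with other safety nets around it. Safety evaluation spans all 14 days, SAE reporting spans them too, and pregnancy can be recorded as a reason for leaving efficacy follow-up. That stands to this extent: a reader might infer that a conception in the window could neither be reported nor come to light, and the documents do not support that. They support a narrower statement, that it lies outside the pregnancy rule and is not actively looked for.

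A reader might also infer that partners of male patients have the stronger rule. They do not. The partner sentence is open-ended in time, but it requires the mother's consent and sets no explicit 24-hour duty. It shows only that the time limit falls on female patients.

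A reader might look to Protocol 10.5.3.1, which counts 30 days after the last dose as on-treatment, and conclude that 8.4 already extends that far. That is an analysis definition to which 8.4 does not refer.

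Finally, the home tests after Cycle 6 might suggest a second gap, because the diary instruction is "Patients should be instructed to bring the diary with them to every visit". That does not show that the diary is the only way a positive result reaches the site. Patient instructions and the consent form are separate material that is not available here, so no conclusion is drawn.

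The objection that few women are affected is fair. It limits the weight of the point but does not remove the inconsistency.

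**Conclusion.** The point holds for female patients. Section 8.4 leaves uncovered the 14 post-treatment days in which criterion 23 still requires contraception, and no scheduled test or follow-up form actively seeks a pregnancy conceived in them. The partial routes reduce the chance that one is missed altogether, but they do not lead to pregnancy reporting or follow-up to outcome.

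The conclusion rests on reading the 8.4 condition literally and on the current text of 5.3, 7.1.5.1, 7.2.2.5.8 and 8.2.2. The documents do not give the number of women of child-bearing potential; the assumption is that it is small, and it could be zero. About 100 patients were planned, and 8 remained on treatment when Amendment 2 revised 8.4, so from that date new wording could reach the post-treatment windows of at most those 8. It is a worthwhile correction to safety reporting, with no bearing on the efficacy results.

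**What to change.** Reconcile 8.4 with 5.3. For female patients, the 24-hour report and the follow-up to outcome should apply to any pregnancy that arises on study treatment or during the post-treatment contraception period given in Section 5.3. Referring to 5.3, and not repeating a number of days, keeps the two sections aligned if either is amended and leaves the length of that period where the protocol already sets it.

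Add to 7.1.5.1 a pregnancy question for women of child-bearing potential at the 30-day safety follow-up, with any positive answer handled under 8.4.

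The cost is a clause in one section, a question at a contact that already takes place, and possibly one or two more pregnancy forms. No visit, test or analysis is added.

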8.5 Warnings and precautions

No evidence available at the time of the approval of this study protocol indicated that special warnings or precautions were appropriate, other than those noted in the provided Investigator's Brochure. Additional safety information collected between IB updates will be communicated in the form of Investigator Notifications. This information will be included in the patient informed consent and should be discussed with the patient during the study as needed.

8.6 Data Monitoring Committee

Not applicable.

8.7 Steering Committee

The steering committee (SC) will be established comprising investigators participating in the trial and Novartis representatives from the Clinical Trial Team.

The SC will ensure transparent management of the study according to the protocol through recommending and approving modifications as circumstances require. The SC will review protocol amendments as appropriate. Together with the clinical trial team, the SC will also develop recommendations for publications of study results including authorship rules. The details of the role of the Steering Committee will be defined in a Steering Committee charter.

9 Data collection and management

9.1 Data confidentiality

Information about study subjects will be kept confidential and managed under the applicable laws and regulations. Those regulations require a signed subject authorization informing the subject of the following:

- What protected health information (PHI) will be collected from subjects in this study
- Who will have access to that information and why
- Who will use or disclose that information
- The rights of a research subject to revoke their authorization for use of their PHI.

In the event that a subject revokes authorization to collect or use PHI, the investigator, by regulation, retains the ability to use all information collected prior to the revocation of subject authorization. For subjects that have revoked authorization to collect or use PHI, attempts should be made to obtain permission to collect follow-up safety information (e.g., has the subject experienced any new or worsened AEs) at the end of their scheduled study period.

The data collection system for this study uses built-in security features to encrypt all data for transmission in both directions, preventing unauthorized access to confidential participant information. Access to the system will be controlled by a sequence of individually assigned

user identification codes and passwords, made available only to authorized personnel who have completed prerequisite training.

Year of birth will be solicited (in the place of exact date of birth) to establish that the subject satisfies protocol age requirements and to enable appropriate age-related normal ranges to be used in assessing laboratory test results.

9.2 Site monitoring

Before study initiation, at a site initiation visit or at an investigator's meeting, Novartis personnel (or designated CRO) will review the protocol and CRFs with the investigators and their staff. During the study, the field monitor will visit the site regularly to check the completeness of patient records, the accuracy of entries on the CRFs, the adherence to the protocol to Good Clinical Practice, the progress of enrollment, and to ensure that study treatment is being stored, dispensed, and accounted for according to specifications. Key study personnel must be available to assist the field monitor during these visits.

The investigator must maintain source documents for each patient in the study, consisting of case and visit notes (hospital or clinic medical records) containing demographic and medical information, laboratory data, electrocardiograms, and the results of any other tests or assessments. All information recorded on CRFs must be traceable to source documents in the patient's file. The investigator must also keep the original signed informed consent form (a signed copy is given to the patient).

The investigator must give the monitor access to all relevant source documents to confirm their consistency with the CRF entries. Novartis monitoring standards require full verification for the presence of informed consent, adherence to the inclusion/exclusion criteria and documentation of SAEs. Additional checks of the consistency of the source data with the CRFs are performed according to the study-specific monitoring plan.

9.3 Data collection

For studies using Electronic Data Capture (EDC), the designated investigator staff will enter the data required by the protocol into the Electronic Case Report Forms (eCRF). The eCRFs have been built using fully validated secure web-enabled software that conforms to 21 CFR Part 11 requirements. Investigator site staff will not be given access to the EDC system until they have been trained. Automatic validation programs check for data discrepancies in the eCRFs and, allow modification or verification of the entered data by the investigator staff.

The Principal Investigator is responsible for assuring that the data entered into eCRF is complete, accurate, and that entry and updates are performed in a timely manner.

Safety laboratory assessments [REDACTED] (blood and tissue) samples drawn during the course of the study will be collected from the investigator sites and sent to the Novartis designated central laboratory for processing. The site staff designated by the investigator will enter the information required by the protocol onto the sample collection eCRF, as well as onto the designated CRO's requisition form. One copy of the requisition form will be forwarded to the central lab along with the corresponding samples with required information (including study number, subject ID, etc.) and one copy will be retained by the site.

PRO data must be recorded by patients onto the electronic tablet device maintained at study site. The site will enter information regarding ePRO collection in the eCRF.

